9.2 Usage

Subjects will use the study contact lens solutions according to the instructions provided by the unmasked coordinator who dispenses the study lens solutions. Each treatment period (Period 1 and Period 2) will last for 30 (\pm 3) days. In addition to dispensing the randomized study contact lens solutions at the respective visit, subjects will be dispensed and fitted with a new pair of their habitual silicone hydrogel contact lenses (including an extra pair of lenses for 2 week replacement between visits, if required for use in each treatment period). The lens dispensations and all planned and unplanned lens replacements must be documented in the source.

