1 SYNOPSIS

Sponsor: Alcon Research, Ltd.
[name]
[name]

Protocol Number: LCO115-P001

Investigational Product: Opti-Free PureMoist (OFPM)

Study Phase:

1 2

3 4

N/A

Protocol Title: Clinical Study of Opti-Free PureMoist for Presbyopic Contact Lens Wearers

Investigator(s)/ No. of Sites: Approximately 8 sites

Center Location(s)/ United States

No. of Subjects Duration of Treatment:

Required: 110 completed 30 ± 3 days per period each product (up to 66 days total)

[figure not shown]
Planned: approximately 120 randomized

(approximately 8 to 20 subjects per site)

Study Population: Current presbyopic soft contact lens wearers (2-week /monthly replacement modalities only) with symptoms of contact lens induced dryness and using a non-Alcon multi-purpose solution.

Objectives: The overall objective of this study is to demonstrate the benefit of OFPM compared to non-HYDRAGLYDE multipurpose contact lens solutions in presbyopes currently wearing soft contact lenses and experiencing symptoms of dryness.

[figure not shown]
[figure not shown]
The primary objective is to demonstrate superiority of OFPM when compared to the subject’s habitual multipurpose solution (HMPS) in reducing symptoms of contact lens induced dryness after 30 days of use, based on responses to the CLDEQ-8 (abbreviated Contact Lens Dry Eye Questionnaire).

Sponsor:

Alcon Research, Ltd.
[name]
[name]

Protocol Number: LCO115-P001

Methodology:

This is a prospective, randomized, crossover (2-treatment, 2-period), observer-masked, and quasi-subject-masked study.

Treatments:

Investigational Product: OFPM

Route of Administration: Thoroughly wet each side of the lens with OFPM solution. Rub the lens for 20 seconds. Rinse each side of the lens for 10 seconds with a steady stream of OFPM solution. Fill your Alcon lens case with fresh OFPM solution.

Refer to MOP for detailed instructions for use in the package insert.

Duration of Treatment: The subject will wear their habitual lens

Sponsor: Alcon Research, Ltd.
[name]
[name]

Protocol Number: LCO115-P001

brand (following manufacturer recommended replacement) on a daily wear basis for 30 ± 3 days using OFPM daily to care for their lenses.

Dosage: Up to 32 cleaning and disinfecting cycles will be used for the study.

Control Article: Habitual Multi-purpose Solution

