5 INTRODUCTION

5.1 Study Rationale and Background

Silicone hydrogel contact lenses pose unique challenges for contact lens care solutions; the solutions must efficiently remove tear lipid deposits and keep the hydrophobic silicone material wettable at the surface.

Opti-Free PureMoist solution is a sterile, buffered, aqueous solution containing sodium citrate, sodium chloride, boric acid, sorbitol, aminomethylpropanol, disodium EDTA (ethylenediaminetetraacetic acid), 2 wetting agents (TETRONIC[®] 1304 and HydraGlyde Moisture Matrix [EOBO-41-polyoxyethylene- polyoxybutylene]) with POLYQUAD (polyquaternium-1) 0.001% and ALDOX (myristamidopropyl dimethylamine) 0.0006% preservatives. HydraGlyde Moisture Matrix is a proprietary multi-functional block copolymer that is primarily designed for wetting and lubricating silicone hydrogel lenses.

The purpose of this study is to demonstrate the benefit of OFPM in presbyopic contact lens wearers with symptoms of dryness as compared to their HMPS. The primary objective is to demonstrate superiority of OFPM compared to the subject's HMPS in reducing symptoms of contact lens-related dryness after 30 days of use, based on responses to the CLDEQ-8 (abbreviated Contact Lens Dry Eye Questionnaire).

This market support study is designed to provide continued reasonable assurance of the effectiveness of OFPM in a specified population of symptomatic presbyopic soft contact lens wearers that fall under the indication of the product. The effectiveness endpoint was identified based on the findings from another post-approval study in a general population of symptomatic soft contact lens wearers who were habitually using Multi-Purpose Solutions to care for their lenses. Biguanide preserved multi-purpose solutions are commonly used disinfection systems in the marketplace and are included in most private label solutions; therefore, they are a reasonable control to the test solution in this study, which is a POLYQUAD/ALDOX preserved multipurpose disinfecting system including a wetting agent that may benefit some soft lens wearers.

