5.3 Potential Benefits

OFPM is indicated for use in the daily cleaning, reconditioning, rinsing, removing protein deposits, reducing lipid deposition, chemical (not heat) disinfection, and storage of silicone hydrogel and soft (hydrophilic) contact lenses as recommended by an eye care practitioner. Based on known product information, in the opinion of Alcon, the benefits gained by the use of the formulation outweigh the risks associated with its use.

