8.1 Inclusion Criteria

1. Age 45-65 (both inclusive) and must sign the informed consent.
2. Current adapted two-week/monthly replacement soft contact lens wearers (at least 2 months) with symptoms of contact lens induced dryness as defined by the Symptomatology (Eligibility) Pre-screening questionnaire.

Note: Subject may be wearing multifocal contact lenses or single vision contact lenses prescribed for monovision or for distance only.
3. Requires a near spectacle ADD of +0.50 or greater.
4. Best corrected visual acuity (BCVA) to 20/30 or better in each eye at distance at Visit 1.
5. Willing to wear lenses for a minimum of 5 days per week 6 hours per day, and attend all study visits.
6. Currently using a non-Alcon MPS to care for their lenses (at least 2 months).
7. Uses digital devices (eg, smart phone, tablet, laptop computer, or desktop computer) for 20 consecutive minutes at least twice a week and willing to continue the same pattern for the duration of the study as assessed at Pre-screening.

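### Does the silicone hydrogel wording in Protocol Section 9.2 put the enrolled population at odds with the population of the claim?

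*Protocol*

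**What the plan says.** Protocol Section 9.2 (Usage) states that "subjects will be dispensed and fitted with a new pair of their habitual silicone hydrogel contact lenses" at the visits where solution is dispensed. It is the only operative text that names a lens material.

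Elsewhere:

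- Inclusion criterion 2 (Section 8.1) admits "Current adapted two-week/monthly replacement soft contact lens wearers (at least 2 months) with symptoms of contact lens induced dryness". No exclusion in Section 8.2 mentions material.
- The overall objective, in the synopsis and again in SAP Section 1.1, concerns "presbyopes currently wearing soft contact lenses and experiencing symptoms of dryness".
- Section 5.1 frames the effectiveness statement for "a specified population of symptomatic presbyopic soft contact lens wearers that fall under the indication of the product".
- The indication in Section 5.3 includes "storage of silicone hydrogel and soft (hydrophilic) contact lenses", so both material types are covered.
- Table 9-1, the visit steps in Sections 10.2.1 and 10.2.2, and the schedules in Protocol Section 2 and SAP Table 10-1 refer to the subject's habitual lenses or lens brand, with no material given.

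**The concern.** The two lens terms are not used as synonyms: the indication lists silicone hydrogel and soft hydrophilic lenses separately. Under Section 9.2 as written, a site with an eligible hydrogel wearer has an instruction it cannot carry out. It might enrol the subject anyway, turn the subject away, or enrol and log a deviation, and about eight sites need not choose alike.

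Material could also matter to the result. Section 5.1 describes the HydraGlyde component as "primarily designed for wetting and lubricating silicone hydrogel lenses", so a smaller benefit in hydrogel wearers is plausible. If they enter, the average effect may fall short of the 3 points used for planning. If sites keep them out, the result speaks only for silicone hydrogel wearers, although the objective speaks of soft lens wearers in general. Either way, the population behind the primary estimate would be less clear than it should be.

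**Working it through.** **The plan's own figure.** Inputs from Protocol Section 11.10 and SAP Section 7: difference 3, SD of paired differences 10, one-sided alpha 0.05, power 80%, 36 per sequence.

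In a 2×2 crossover the treatment effect is tested by comparing period differences between sequences, a contrast of 2 × 3 = 6 with SD 10:

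n per sequence = 2 × (1.645 + 0.842)² × 10² / 6² = 34.4, rounded up to 35.

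For 36 per sequence (72 subjects), the noncentrality is 3 / (10/√72) = 2.55 on 70 degrees of freedom, and power is 0.809. The stated figure reproduces. With the 110 completers planned in Section 8, the noncentrality is 3 / (10/√110) = 3.15 and power is 0.931.

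**If hydrogel wearers enrol.** Assumption, not in the documents: a fraction p wear hydrogel lenses and gain nothing, the SD stays at 10, and the mean effect is 3(1 − p).

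| p | mean effect | power, 72 subjects | power, 110 subjects |
|---|---|---|---|
| 0 | 3.0 | 0.809 | 0.931 |
| 10% | 2.7 | 0.734 | 0.879 |
| 20% | 2.4 | 0.645 | 0.804 |
| 30% | 2.1 | 0.548 | 0.707 |

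The 110 column is the relevant one, because that is the number the trial plans to complete.

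**If sites screen them out.** If recruitment still reaches 110, power stays at 0.931 for an effect of 3. If the exclusions reduce completers to 99, 88 or 77 (90%, 80% or 70% of 110), power is 0.906, 0.874 or 0.832.

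**What the wording of Section 9.2 controls.**

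1. *Who enters.* Section 8 says the complete criteria are in Sections 8.1 and 8.2. Section 10.2.1, steps 8 and 9, qualifies and randomizes on those criteria, and Section 10.4 screen-fails only those who do not meet them. Section 9.2 gives no ground to exclude anyone.
2. *What is dispensed.* Step 10 of Sections 10.2.1 and 10.2.2 can be followed for a wearer of either material.
3. *Who is analysed.* The full analysis set (Protocol Section 11.2.2, SAP Section 2.2) is all randomized subjects exposed to at least one study solution. Material plays no part.
4. *How treatments are compared.* Each subject keeps the same habitual lens brand in both periods, so material is balanced within subject and cannot bias the contrast or the type I error.

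The losses in the table therefore come from inclusion criterion 2. Putting soft lenses in place of silicone hydrogel in Section 9.2 would leave every row as it is.

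**The case for a change.** The strongest case for acting is that Section 9.2 is addressed to sites, departs from eligibility on the attribute the rationale singles out, and was left as it stood when Amendment 1 was issued during study execution. A wording correction is cheap, and a by-material estimate of the primary contrast would show whether the benefit extends to hydrogel wearers.

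The inconsistency stands: for an eligible hydrogel wearer, Section 9.2 cannot be followed to the letter, and the passages do need to be read together. The consequences do not follow as strongly:

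- Divergent handling by sites is conjecture, and it runs against the eligibility and visit sections.
- Zero benefit in hydrogel wearers is the extreme case. Section 5.1 says the component is primarily, not solely, aimed at silicone hydrogel, names a second wetting agent, and bases the choice of endpoint on a study in a general population of symptomatic soft lens wearers. Nothing ties the 3-point difference to silicone hydrogel alone.
- A by-material estimate would be descriptive and imprecise. Text following the primary analysis and the exploratory objectives is withheld from the public documents, so its absence cannot be asserted. Habitual lens information is already summarized at baseline (Protocol Section 11.3, SAP Section 3). Whether material is recorded as such is not stated.

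**Conclusion.** This is a clerical slip: one misplaced description of the lenses in a usage section, set against eligibility, objective, rationale and indication that agree with one another. The enrolled population and the population of the claim are both symptomatic presbyopic soft lens wearers.

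Correcting the phrase would change no enrolment rule, analysis set, model, alpha or sample size, so its effect on power is nil. The separate question of a weaker effect in hydrogel wearers would cost power only to the extent assumed. With no benefit at all in 20% of subjects, power at 110 completers would still be 0.804.

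The conclusion assumes that the manual of procedures and the Deviations and Evaluability Plan, neither of which is in the public documents, do not restrict lens material. If the protocol is reopened for another reason, Section 9.2 and inclusion criterion 2 can be brought into line, but nothing in the planned inference depends on it.

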9.3 Accountability Procedures

Designated unmasked site personnel will dispense the study contact lens solutions (re-labeled OFPM and the site/subject purchased commercially labeled HMPS) in accordance with their assigned subject ID number and the randomization treatment order allocated to them. The identity of the test product will not be revealed to the subject and the order of use of the test and control products will not be revealed to the Investigator. It will not be possible to maintain full subject masking due to the nature of the cleansing devices, but the brand name will be masked for the test solution. During the study, the investigational site must maintain records of study treatment dispensation and collection by the unmasked personnel for each subject. This record must be made available to the designated study monitors for the purposes of verifying the accounting of clinical supplies. Any discrepancies and/or deficiencies between the observed disposition and the written account must be recorded along with a detailed explanation. Study contact lens cleaning devices associated with a device deficiency or with any product-related AEs must be returned to the Sponsor or manufacturer (for comparator/reference product). Refer to Section 12 for additional information on the reporting of device deficiencies or product-related AEs.

At the conclusion of the study, the Investigator will be responsible for returning all used and unused study supplies unless otherwise instructed by the Sponsor.

Upon receipt of the test products (OFPM test solution kits) from Alcon, the unmasked coordinator will conduct an inventory. During the study, the unmasked coordinator must maintain records of study treatment dispensation and collection for each subject including study solutions (test OFPM or purchased control HMPS). This record must be made available to the study monitor for the purposes of verifying the accounting of clinical supplies. Any discrepancies and/or deficiencies between the observed disposition and the written account must be recorded along with an explanation. At the conclusion of the study, the Investigator

will be responsible for returning all used and unused study supplies unless otherwise instructed by the Sponsor.

9.4 Subject Confidentiality and Methods Used to Minimize Bias

The Investigator must ensure that the subject's anonymity is maintained throughout the course of the study. In particular, the Investigator must keep an enrollment log with confidential identifying information that corresponds to the subject numbers and initials of each study participant. At the end of the clinical study, the Sponsor will collect a copy of the enrollment log without any identifying subject information. All documents submitted to the Sponsor will identify the subjects exclusively by subject ID and demographic information. No other personally identifying information should be transmitted to the Sponsor.

The intent of masking is to limit the occurrence of conscious and unconscious bias in the conduct and interpretation of the clinical study. Bias could arise from the influence that the knowledge of a specific treatment assignment may have on the recruitment and allocation of subjects, their subsequent care, the assessment of end points, the handling of withdrawals, and so on. The essential aim of masking, therefore, is to prevent identification of the test article(s) by the Investigator, subject, and others associated with the conduct of the study until all such opportunities for bias have passed.

This study is Investigator-masked and subject quasi-masked (masked to test solution brand only), with subjects randomized to the order in which they will use OFPM and their HMPS for 30 ± 3 days each. The Investigator will not be aware of the specific treatment being administered and the subject will not be aware of the brand of the test solution. Alcon study personnel will be masked, with the exception of the following: Study monitor, Lead CSM, and person responsible for generating the randomization schedule. This level of masking will be maintained throughout the conduct of the study. Subjects will be assigned treatment order based on the randomization schedule; it will be blocked to ensure a balance of study treatment allocations within investigational sites. The randomization scheme will be generated and maintained by the Sponsor. In the event of a medical emergency where the knowledge of subject treatment is required, an individual Investigator will have the ability to unmask the treatment sequence assignment for a specific subject.

10 STUDY PROCEDURES

10.1 Outline of Study

[figure not shown]
Prior to informed consent and scheduling the Screening visit, subjects will be given the Pre-screening Questionnaire (Symptomatology Questionnaire, Digital Device Use assessment and HMPS Identification Tool). These may be administered via a combination of phone, email, or in person; (Note: the HMPS Identification Tool is visual). Once the subject completes the questionnaire and the replies indicate the subject to be eligible to proceed then informed consent must be obtained from the subject before any procedure specified by this protocol is initiated, including Screening procedures at Visit 1. The original signed informed consent must be maintained with the subject's file whether they pass or fail Screening. A copy of the signed informed consent form will be provided to the subject. Data from the Pre-screening Questionnaire will not be entered into to the electronic case report forms (eCRFs) but will stay in the subject file as source documents for monitoring of both randomized subjects and screen failures. Those who pass pre-screening and sign informed consent may attend the Screening visit (Section 10.2.1).

Subjects who are scheduled to attend the Screening visit must have a new bottle of the HMPS identified during pre-screening ready for possible dispensing at the end of the Screening visit after randomization. This can be accomplished in two ways for the study:

- 1) The subject purchases a new bottle of the HMPS and brings it to the Screening visit. In this case the subject will be reimbursed for their purchase. The unmasked coordinator must confirm the solution purchased was the HMPS identified during pre-screening and that it is not expired. If HMPS is randomized to be used for Period 2, the site will maintain the purchased HMPS at the site for the subject until Period 2;
- 2) The site purchases the subject's HMPS and dispenses to the subject according to the randomization schedule.

Adverse events (AEs)/serious adverse events (SAEs) and device deficiencies will be assessed and reported at all scheduled and unscheduled study visits for each subject from the time of informed consent.

Figure 10-1 Diagram of Study Design

10.2 Visits and Examinations

10.2.1 VISIT 1 – SCREENING/BASELINE & PERIOD 1/DAY 1 VISIT

1.	If the pre-screened eligible subject was asked to purchase a new bottle of their own HMPS, then the site should ensure the HMPS purchased matches the HMPS identified at pre-screening and is not expired. If this does not occur, the Screening visit should be rescheduled.
2	Have the subject read, sign, and date the IEC/IRB approved informed consent document. Additionally, have the individual obtaining consent from the subject and a witness, if applicable, sign and date the informed consent document. Provide a photocopy of the signed document to the subject and place the original signed document in the subject's chart.
3	Enter the subject into the EDC system to obtain a subject ID. Note: A subject ID is needed for all subjects who sign an informed consent form (including screen failures).
4	Obtain demographic information, medical and lens/lens care history (including confirmed HMPS), typical activities performed while being active, concomitant medications/ changes in concomitant medications including information on all medications used within the past 30 days. Include herbal therapies, vitamins, and all over-the-counter as well as prescription medications.
5	Have subject complete Subjective Questionnaires based on habitual lenses and care system (CLDEQ-8, [REDACTED] [REDACTED])
6	Remove lenses and perform subjective (manifest) refraction. For details refer to MOP.
7	Perform BCVA assessment. For details refer to MOP.
8	Perform biomicroscopy assessments using slit-lamp examination scales. For details refer to MOP. Review inclusion/exclusion criteria to determine if the subject qualifies to be randomized into the study.
9	Only for subjects qualifying to be included in the study, confirm randomization by entering details of eligibility into the EDC system and obtain study solution assignment for each period.

10	Dispense a new pair of habitual lenses and perform Snellen VA with new lenses being dispensed at the visit. For details refer to MOP. For two-week replacement lens wearers, provide the subject an extra pair of study lenses for replacement at 2 weeks. Contact the subject at approximately 15 ± 1 days of the study period to remind the subject to replace their lenses and document date of replacement in the source.
11	Unmasked coordinator to assign/dispense the study lens care solution for Period 1 per randomization scheme. 1) HMPS purchased by the subject or provided by the site –or- 2) Investigational Masked OFPM Kit with Kit #. Educate on instructions for use.
12	Assess and record any adverse events (AEs) that are reported or observed from the time of informed consent (see Section 12).
13	Record any device deficiencies that are observed or reported.
14	Schedule Visit 2 (Period 1 Follow-up) to take place on Day 30 ± 3 days (scheduled 29 (± 3) days after Visit 1. Provide subject with Visit 2 reminder instructions: 
 The subject should bring the used lens case for the study period, along with their dispensed study lens care product used during the study period.

10.2.2 VISIT 2 – PERIOD 1/Day 30 & PERIOD 2/DAY 1

1	Document wear time compliance (days, hours) and lens care compliance. Collect used study lens care product from the subject.
2	Obtain information on any changes in medical health and/or the use of concomitant medications since Visit 1.
3	Have subject complete the Subjective Questionnaire based on lenses worn and study solution used during the 30 day study period (CLDEQ-8, [REDACTED] [REDACTED] [REDACTED])
4	Conduct Snellen VA with worn lenses. For details refer to MOP.
5	[REDACTED]

6	Remove lenses and perform biomicroscopy assessments using slit-lamp examination scales. For details and order of staining procedures, refer to MOP.
7	Perform subjective (manifest) refraction assessment and BCVA assessment (as needed). For details refer to MOP.
8	Assess and record AEs that are observed or reported (see Section 12).
9	Record any device deficiencies that are observed or reported.
10	Dispense a new pair of habitual lenses and perform Snellen VA with new lenses being dispensed at the visit. For details refer to MOP. For two-week replacement lens wearers, provide the subject an extra pair of study lenses for replacement at two weeks. Contact the subject at approximately 15 ± 1 days of the study period to remind the subject to replace their lenses and document date of replacement in the source.
11	Unmasked coordinator to assign/dispense the study lens care solution for Period 2 per randomization scheme. 1) HMPS purchased by the subject or provided by the site –or- 2) Investigational Masked OFPM Kit with Kit #. Educate on instructions for use.
12	Schedule Visit 3 (Period 2 Follow-up) to take place on Day 30 ± 3 days (scheduled 29 (± 3) days after Visit 2. Provide subject with Visit 3 reminder instructions: 
 The subject should bring the used lens case for the study period, along with the dispensed study lens care product used during the study period.

